### **Motor Control:**

These tests are will be used to study movements of the upper extremity. One or more of these tests, commonly involving imagined movements, will be carried out at up to 7 recording sites and will take 5 to 10 minutes at each site. All experimental protocols and variables will be under computer

Date: February 19, 2023

Principal Investigator: [name].

Application Number: NA\_00079932

control and will be carried out in healthy subjects, patients not going to surgery, or patients undergoing functional stereotactic procedures. In patients undergoing extra-operative testing and recordings of electrical signals, basic sensory and motor testing will be part of routine care. The proposed studies represent more involved sensory and motor protocols, and these protocols will not be part of standard care.

- 1) Subjects will be studied while performing actual upper extremity movements in response to a light cue. The nature of the cued movement will be indicated by verbal commands such as 'make a fist' at the start of a trial consisting of several presentations of the cue. Imaginary movements will be carried out at each joint in the upper extremity contralateral to the recording on a verbal command such as 'imagine that you are making a fist without moving'. EMG recording and movement sensors such accelerometers will be employ.
- 2) Torque motor: In the motor testing, torque motors and an articulated handle will be used to measure arm movements to visual targets in a planar work space in front of the chest. The patient's arm will be supported in a sling throughout trials, which will last less than 10 minutes. This device will allow us to examine neuronal signals related to the motor learning and error detection during arm movements.
- 3) Motor Tracing: Subjects will be instructed to use finger to trace targets shown on a touch display. This task may be done before, during or after the operation to evaluate the controllability and stability of patient's motor function. Healthy participants serving as controls may also perform this task.

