### **Objective II:**

Objective II is to test the hypothesis that actual and imagined movements and movement disorders are the result of ongoing and movement related activity of single neurons, local field potentials and EEG activity recorded from cortical structures and deep nuclei (basal ganglia and thalamus).

Date: February 19, 2023

Principal Investigator: [name].

Application Number: NA\_00079932

The primary outcome is to establish the effect of ongoing and evoked spike, local field potential and EEG activity recorded from cortical and deep nuclei upon movement disorders such as tremor, Parkinson's disease, dystonia and dyskinesia. Analysis of these results for functional connectivity will allow us to characterize networks involved in movement disorders.

Secondary outcomes will include determination of the influence of actual and imagined movements upon ongoing and movement related spike, local field potential, and EEG activity recorded from cortical and deep nuclei.

We also will investigate the effects of direct cortical stimulation with electrical pulses on the motor cortex and other cortices by measuring electrophysiological signals, and will evaluate stimulation effects on disease symptoms.

Additionally, we will determine whether scalp-applied tDCS over the motor cortex also results in modulating single neuron spiking activities or changes in cortical phase –amplitude coupling.. This will be helpful in providing more understanding of the mechanisms of action of DBS and tDCS, and may indicate the usefulness of integrating the two different types of brain stimulation in the future.

Other secondary outcomes will determine whether motor learning or adaptation are the result of ongoing and movement related spike, local field potential and EEG activity recorded from cortical and deep nuclei.

Other secondary outcomes will also include the determination of the mechanisms of speech characteristics as coded in the basal ganglia-thalamocortical network during production and auditory processing of speech based on specific task related spike, local field potential, and EEG activity recorded from cortical and deep nuclei.

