### ***Objective II and III:***

Our primary outcome variables will identify the functional connectivity within networks of cortical and subcortical structures which subserve movement. We will determine functional connectivity between structures activated during actual and imagined movement. Recordings will be made of single neuron and LFP activity in the basal ganglia, thalamus and cortex during actual and imagined movements.

Our secondary outcome variables will identify the functional connectivity within networks of cortical and subcortical structures which subserve movement disorders. We

Date: February 19, 2023

Principal Investigator: [name].

Application Number: NA\_00079932

will determine functional connectivity between structures activated during disordered movement. We will also determine the effects of tDCS on single and multiunit activity in the recorded subcortical structures. Recording and analysis techniques will be similar to those under the primary outcome of this objective.

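### As written, actual movement is triggered by a light cue but imagined movement by a spoken command, and no alignment event is given for imagery

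*Combined protocol and SAP*

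**What the plan says.** Section 4 (Study Procedures, Motor Control, item 1) describes both tasks.

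- **Actual movement, trigger:** "Subjects will be studied while performing actual upper extremity movements in response to a light cue".
- **Actual movement, role of the spoken command:** "The nature of the cued movement will be indicated by verbal commands such as 'make a fist' at the start of a trial". A trial then contains several light cues.
- **Imagined movement:** "Imaginary movements will be carried out at each joint in the upper extremity contralateral to the recording", and this is done "on a verbal command such as 'imagine that you are making a fist without moving". No light cue is mentioned.
- **Sensors:** "EMG recording and movement sensors such accelerometers will be employ".

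The outcome that uses both tasks appears twice. Section 7 (Study Statistics, Objective II and III) lists it under the primary outcome variables: "We will determine functional connectivity between structures activated during actual and imagined movement". Section 2 (Objective II) places the influence of actual and imagined movement on recorded activity among the secondary outcomes. The same section also sets out to study how speech is coded in the basal ganglia-thalamocortical network "during production and auditory processing of speech".

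The opening of Section 7 provides paired analysis for within-subject comparisons in general terms and calls the study exploratory. It names no contrast between actual and imagined movement.

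**The concern.** A patient who imagines a movement on hearing a sentence is doing two things at once: processing speech and imagining. If the spoken command is the trigger, the two occur together in every imagined trial, and no later analysis can separate them. The actual-movement trials have a different companion, a response to light.

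Two results would be affected. Within the imagined condition, a site or connection could be read as part of an imagery network when it reflects hearing and understanding the command. If the two conditions are compared, the difference would contain light versus speech as well as movement versus imagery.

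The first matters particularly here because the protocol itself treats auditory processing of speech as something coded in the network under study. In surgical patients these are awake recordings from deep nuclei that cannot readily be repeated, so a cue problem built into the task stays in the data.

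**Working it through.** The documents give no sample size, effect size, variance or cue schedule for the motor tasks, so there is no figure to reproduce. The check is a comparison of the texts.

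**1. Are the triggers the same?** For actual movement the trigger is the light. The spoken command comes once, at the start of a trial of several cues, and says which movement to make, so it does not equalise the triggers. For imagined movement the only event named is the spoken command. Read literally, the triggers differ.

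**2. Does another section settle it?** Section 3 (Background, and its Objective II: Motor Control part) says only that patients will be asked to carry out imagined or actual movements. The Motor Control section says that protocols and variables are under computer control, but gives no cue schedule. No section gives a matched cue, a cue-only condition, or the event to which imagery recordings are aligned.

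**3. Can the sensors supply a time reference?** EMG and accelerometers register overt movement. They can time the onset of an actual movement and show that an imagined one was not acted out. They cannot time the onset of imagery, so the cue is the natural reference for imagined trials.

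**4. How long is the spoken cue?** The example command has nine words. At an assumed 2 to 3 words per second (the documents give no rate), it lasts 9/3 = 3 s to 9/2 = 4.5 s. The text does not say whether time zero is the start or the end of the sentence. The length of the analysis window is not given either, so the share of it taken up by speech cannot be calculated.

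**5. Which measures are affected?** Section 3 defines activation by firing rate, EEG frequency and spectral power. It identifies joint processing by correlation, coherence and causality between sites, and Section 7 (Objective I) uses the same family of connectivity measures. All are computed from signals recorded around the cue. If the cue is a sentence, its processing enters every one of them.

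**6. How much recording is involved?** The Motor Control section says the tests commonly involve imagined movements, at up to 7 sites for 5 to 10 minutes each. At 7 sites that is 7 × 5 = 35 to 7 × 10 = 70 minutes over all the motor tests done. The part spent on imagery is not stated.

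**The case against.** **The sentence has another reading.** Both tasks sit in one numbered item, and the imagery command is phrased like the command that opens an actual-movement trial, which is expressly not the trigger. The imagery command may be a start-of-trial instruction too, with the light still triggering each repetition. This stands as a possible reading. A reader might infer that the study certainly mixes cue type with movement; the text does not establish that. It neither states nor excludes a light cue for imagery, so staff could run either version.

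**No contrast is prespecified.** A reader might infer that the primary outcome is a comparison of actual with imagined movement. Sections 2 and 7 can equally be read as describing the network in each condition separately. This also stands, and it limits the light-versus-speech problem to comparisons made under the general paired analysis. It does not remove the problem within the imagined condition, where speech processing and imagery remain together.

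**The rank of the outcome is unsettled.** Section 7 makes it primary and Section 2 secondary, so the point should not be weighed as if the primary status were clear.

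**Loose timing does not by itself erase the result.** A reader might infer that uncertain imagery onset would wash out the imagined response. That applies to averages time-locked to the cue. Onset variation shared by simultaneously recorded sites leaves their relative phase largely intact, so it does not carry over directly to coherence, nor to spectral power. The documents also give no onset variability from which to calculate a loss.

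**Conclusion.** The concern holds in a limited form. As literally written, actual movement is triggered by light and imagined movement by a spoken command, and imagery has no alignment event. If run that way, activity and connectivity in imagined trials include auditory-verbal processing, and any comparison of the two conditions also carries light versus speech.

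This rests on three things: the literal reading of item 1; the protocol's own premise that speech processing is coded in the network studied; and, for the second part only, that someone makes the comparison. The size of the effect cannot be calculated from the documents. The exploratory label does not answer the point, because it concerns what the recordings contain and not how strictly they are tested.

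The change is worth making before further recordings, since it costs little and the gap cannot be repaired in analysis. Confidence is moderate because the intended task may already use a common cue.

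**What to change.** In Section 4 (Motor Control, item 1), state that:

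- both the 'make' and the 'imagine' instructions are spoken at trial start only;
- the same light cue triggers every actual and every imagined repetition;
- recordings in both conditions are aligned to that cue;
- the EMG already recorded is used to flag imagined trials with muscle activity, and these are excluded.

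Sections 2 and 7 should also agree on whether the outcome is primary or secondary.

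**Cost:** a few sentences and a change to the task script, with no new equipment. Excluding trials loses some data within the 5 to 10 minutes per site, and replacing them would take time.

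**What it does not do:** a common cue removes the light-versus-speech difference and takes the sentence out of the imagery window. It does not remove variation in how quickly patients begin to imagine. Nor does it separate the response to the light from movement or imagery within each condition; that would need a cue-only condition.

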### **Sensory Processes and Motor Control: Psychological Testing:**

#### Neuropsychological and Psychological Tests:

Many patients with movement disorders involved in these protocols will undergo extra-operative pencil and paper psychological tests or structured interviews, in addition to those which are required for clinical assessment. In total, the extra-operative testing of these patients may include a standard neuropsychological battery of tests of intelligence, language, motor function, learning, memory, and attention. Patients may also be tested with a psychological battery including measures of personality, depression/mood, fear/ anxiety, and avoidance behaviors. Many of these same tests will be carried out in healthy subjects.

Patients with movement disorders will be assessed by quality of life and disability indices specific to their condition, as part of standard clinical assessment. In addition, they may undergo intra-operative studies using validated, abbreviated protocols for some of these extraoperative tests. These will include tests of attention, learning, memory, fear/anxiety, and avoidance behaviors.

#### Patients Undergoing Surgery:

For patients involved in extra-operative studies there may be one preoperative and one postoperative testing session, each lasting approximately 2 hours. The intraoperative procedures will last approximately 1 hour and twenty minutes during the time that the patient is in surgery.

Date: February 19, 2023

Principal Investigator: [name].

Application Number: NA\_00079932

Patients Not Eligible for Surgery, choosing not to have surgery, or already having had surgery:

After consent is obtained, there will be at least one visit lasting approximately 4 hours.

Healthy Participants and Chronic Pain Patients with Knee Osteoarthritis and Chronic Pain Patients with Chronic Widespread Pain, Fibromyalgia, and with PTSD:

These participants will have one visit for consenting and education to determine eligibility. Then, there will just one additional visit lasting approximately 2 hours.

During one laboratory session we will ask healthy participants to provide three saliva samples; one at the beginning of the session, one immediately after completing the behavioral task, and one 30 minutes after the behavioral task. At the beginning and end of this same session, we will ask subjects to provide blood samples, which will be obtained by ICTR-trained staff of the [name] lab by venipuncture. Each sample will be one 8.5 ml volume acid citrate dextrose tube and one serum separator tube of blood. Saliva and blood samples will be stored at no more than -80 °C by the Johns Hopkins Genetic Core Resources Facility for later analysis of cortisol, cytokines and SNPs. All data relating to genetic information, including saliva and blood tube sample containers will be deidentified at origin and assigned a subject code corresponding to the subject's behavioral and imaging data. This will minimize the likelihood of discovery of personally identifiable information.

## 5. Inclusion/Exclusion Criteria

Patient Inclusion/Exclusion Criteria:

Intra-operative studies may be carried out in patients undergoing functional stereotactic procedures for the treatment of movement disorders or pain. All these subjects must meet standard medical and anesthetic criteria to be a candidate for these surgical procedures. If the subjects do not meet these criteria then they are not a candidate for surgery and so will not be a candidate for these intraoperative studies.

Extra-operative studies may be carried out in healthy subjects and patients not candidates for surgeries. They may also be carried out pre- and post-operatively in subjects undergoing functional stereotactic procedures.

Exclusions for intra- and extra-operative research tests will include patients with significant language, hearing, or cognitive impairment, and non-English speakers.

The tDCS and direct cortical stimulation testing procedures will not be performed on patients with seizure disorders, or a history of having a seizure. However, some studies suggest that cathodal tDCS may be a potential therapeutic tool in epileptic disorders, particularly in drug-resistant patients (Fregni et al., 2006; Yook et al., 2011 ).

Healthy Participant Inclusion/Exclusion Criteria: All healthy individuals between 18 and 80 years of age will be eligible to serve as healthy participants. Patients with a history of significant neurological or non-neurological illnesses will be excluded. Gender or age matching will not be used to

Date: February 19, 2023

Principal Investigator: [name].

Application Number: NA\_00079932

counterbalance the population of healthy controls. Participants will be asked to submit to urine drug analysis, those who subsequently test positive for illegal drugs or refuse testing will be excluded.

**Patients with chronic pain from knee osteoarthritis:** All individuals between 18 and 80 years of age with chronic pain (pain  $\geq 45$  of the past 90 days and pain intensity  $\geq 3/10$  for the past 24 hours) from knee osteoarthritis will be eligible for this portion of the study. Patients with a history of significant neurological illnesses will be excluded. Participants will be asked to submit to urine drug analysis, those who subsequently test positive for illegal drugs or refuse testing will be excluded.

**Patients with chronic pain from chronic widespread pain or fibromyalgia:** All individuals between 18 and 80 years of age with chronic pain (pain  $\geq 45$  of the past 90 days and pain intensity  $\geq 3/10$  for the past 24 hours) from chronic widespread pain or fibromyalgia (defined as pain present in 4 of 5 areas of the body (right leg; left leg; right arm; left arm; neck, upper and lower back) and present in at least 7 painful sites) will be eligible for this portion of the study. Patients with a history of significant neurological illnesses will be excluded. Participants will be asked to submit to urine drug analysis, those who subsequently test positive for illegal drugs or refuse testing will be excluded.

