## 2. Objectives

### **Objective I:**

Objective I is to assess the hypotheses that the cortex and deep nuclei of the brain (e.g. thalamus, ventral striatum) are involved in signaling acute pain, and that abnormalities of this region are responsible for many of the symptoms found in neuropathic pain.

The primary outcome is to assess the effect of painful and nonpainful somatic stimuli upon ongoing and evoked spike, local field potential, and EEG activity recorded from cortical and deep nuclei in response to painful stimuli. Non-invasive EEG will be used in healthy subjects and chronic pain patients. Analysis of these results for functional connectivity will allow us to characterize networks subserving pain processing and their disruption or augmentation in chronic pain.

The secondary outcome is to determine the effect of attention, along with cognitive and learning tasks involving somatic stimuli upon ongoing and evoked activity, local field potential and EEG activity recorded from cortical and deep nuclei. Non-invasive EEG will be used in healthy subjects and chronic pain patients. Analysis of these results for functional connectivity will allow us to characterize networks subserving pain related cognitive processes and their disruption or augmentation in chronic pain.

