### **Recruitment:**

**Patient Populations:** Patients will be recruited from new, prior, and current patients of the PI in the Johns Hopkins Outpatient Center or through posted advertisements. Patients attending surgeries will be consented for surgery at the visit before the preoperative visit. The research protocol will be discussed at the preoperative visit.

**Chronic Pain Patients:** Knee OA patients will primarily be referred to the study from a study at Hopkins Bayview (Co-I: [name]), while patients with PTSD and comorbid chronic pain will be referred from the Hopkins Anxiety disorder clinic (Co-I [name]) the Hopkins Followup Clinic for the Medical ICU (CoI, [name]). They will call the study team and the study team will describe the study, answer questions, screen the patient and schedule a time for them to come in to the lab to obtain consent if they elect to proceed. All chronic pain patient groups will be recruited from pain clinics in the greater Baltimore area, including those at Johns Hopkins and University of Maryland, by flyers and brochures. Flyers and brochures will also be given to patient advocacy and support groups.

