## 7. Study Statistics

This is a single institution, long-term exploratory study to understand forebrain networks of human sensory processing and motor control. Specifically Objective I will address cortical and subcortical networks of sensory signaling and processing, while Objective II will address the cortical and subcortical networks involved in motor control.

Due to the exploratory nature of the study, all outcome data will be collected regardless of data type such as electrophysiological responses, or timing, or the questionnaires related psychological function. In general, data will be summarized using descriptive statistics and graphical techniques. Within and between-subjects comparisons will use paired and unpaired analysis, respectively. Longitudinal outcomes or repeated measures will be considered and possibly be analyzed using generalized linear model. Correlation coefficient or concordance correlation coefficient will be used to estimate correlation between two outcomes.

The outcome measures for the three objectives are indicated below:

Primary and secondary outcome variables:

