### ***Objective I:***

Under Objective I we will determine functional connectivity between structures at which single neuron and LFP responses occur in response to painful laser stimuli. Secondary outcome variables will address cognitive processes related to sensory stimuli and the networks which subserve them. These networks will be defined by measures of functional connectivity between electrode sites such as correlation, coherence, and causal (directed) interactions.

Network characteristics will be estimated by measures of connectivity at the time of laser stimuli between sites such as correlation, coherence, functional connectivity, and causal interactions.

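### Healthy controls are unmatched on age and sex and Section 7 names neither as a model term, so the chronic-pain-versus-healthy comparison implied by Objective I is open to confounding by both

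*Combined protocol and SAP*

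**What the plan says.** Section 5 (Healthy Participant criteria), in a sentence that runs over a page break, states that "Gender or age matching will not be used to" balance the healthy control population. Healthy participants and the two pain groups with stated criteria (knee osteoarthritis; widespread pain or fibromyalgia) share age limits of 18 to 80 years.

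Section 2, Objective I, makes the stimulus effect the primary outcome: "The primary outcome is to assess the effect of painful and nonpainful somatic stimuli" on recorded activity. It adds that "Non-invasive EEG will be used in healthy subjects and chronic pain patients" and that the connectivity analysis should "characterize networks subserving pain processing and their disruption or augmentation in chronic pain".

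Section 4 gives the sources. For patients, "All chronic pain patient groups will be recruited from pain clinics in the greater Baltimore area", along with referrals from other studies and clinics. Healthy participants are to include spouses and other relatives of patients, and may also be employees and students of the institution.

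On analysis, Section 7 says: "Within and between-subjects comparisons will use paired and unpaired analysis, respectively". A generalized linear model is mentioned only as a possibility, for longitudinal or repeated measures, with no terms listed. The Objective I paragraph of Section 7 reads: "Under Objective I we will determine functional connectivity between structures at which single neuron and LFP responses occur in response to painful laser stimuli". It names no group comparison. Age and sex are listed as recorded data only for the speech-testing record (Section 4 and the Data Sharing part of Section 7).

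**The concern.** Disruption or augmentation in chronic pain can only be judged against people without it, so the Objective I aim implies a patient-versus-healthy contrast. Leaving controls unmatched is acceptable if the analysis adjusts. Here matching is expressly declined and adjustment is not specified.

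If the groups differ in age or sex, and the EEG or connectivity measure varies with either, an unadjusted difference appears even when pain has no effect. A larger sample does not shrink that bias; it only makes the spurious difference more likely to look convincing. A purely descriptive comparison carries the same bias, so the lack of a stated significance level does not remove the problem.

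**Working it through.** **Text check.** Neither Section 7 nor any other part of the documents names an age term, sex term, covariate set, stratification or weighting for a group comparison. Shared 18 to 80 limits fix the range, not the distribution within it. Section 5 also excludes healthy volunteers for significant non-neurological illness, whereas the two pain groups with stated criteria are excluded only for neurological illness. That could plausibly make controls younger, though this is an inference.

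**No figure to reproduce.** The plan gives no alpha, power, effect size or group size for this contrast. The only count, seventy patients for sensory testing, is not split by group and has no control number.

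**Assumed inputs.** 20 or 35 per group; two-sided 5% test; no true group effect; ages from normal distributions truncated to 18 to 80, with patients at nominal mean 60 (SD 10) and controls at nominal mean 35, 45, 55 or 60 (SD 14); age effect 0.1 or 0.2 SD per decade; where sex is included, 80% v 50% women and a 0.3 SD sex effect.

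**Bias.** Age bias = slope per decade × gap in decades. After truncation the patient mean is 59.4 and the control means are 38.0, 45.6 and 54.0.
- Smallest: 0.1 × (59.4 − 54.0)/10 = 0.05 SD.
- Largest: 0.2 × (59.4 − 38.0)/10 = 0.43 SD.
- Sex bias: 0.3 × (0.80 − 0.50) = 0.09 SD, added if it acts in the same direction as age and subtracted if it opposes.

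**False-positive rate, hand check.** With SE = √(2/n), n = 35 gives √(2/35) = 0.239. For bias 0.43, 0.43/0.239 = 1.80, and Φ(1.80 − 1.96) is about 0.44. Simulation, which also counts the spread that age adds to the outcome, gives 42%.

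**Simulation (6,000 studies per setting), unadjusted test, age only.** Each pair is for slopes 0.1 / 0.2.

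| Control nominal mean age | n = 35 | n = 20 |
|---|---|---|
| 35 | 14.2% / 42.2% | 9.5% / 25.7% |
| 45 | 9.0% / 19.9% | 6.8% / 13.2% |
| 55 | 5.0% / 7.1% | 5.4% / 6.5% |
| 60 | 5.7% / 5.3% | 4.9% / 4.5% |

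With the sex effect added in the same direction, control means 35 to 55 give 9% to 55% (n = 35) and 7% to 34% (n = 20). With it opposing, they give 5% to 27% and 5% to 17%. Sex alone at 0.3 SD gives 7.1% (n = 35) or 5.3% (n = 20).

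**Adjusted.** With age and sex in the model the rate is 4.3% to 5.6% in all these settings. It is 4.7% to 5.6% when a mild quadratic age effect (0.05 SD per decade squared) is present and only linear age is fitted.

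**Second parameterisation.** Take an outcome-age correlation of 0.2, an age gap of 1 SD and the same sex inputs. Bias is then 0.2 × 1 + 0.3 × 0.3 = 0.29 SD. Unadjusted false positives are 14.5%, 21.8% and 39.6% at 20, 35 and 70 per group; adjusted, they are 4.8%, 5.0% and 4.7%. The unadjusted rate rises with sample size, as expected of a fixed bias.

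**The case against.** The best defence is that no analysis in the plan is shown to be wrong. Section 7 opens: "This is a single institution, long-term exploratory study to understand forebrain networks of human sensory processing and motor control". It sets no alpha, sample size or model terms for any comparison, so a missing age or sex term is one instance of general brevity. Unpaired here means independent groups and does not rule out regression. The primary outcome of Objective I is a within-subject contrast, and the group comparison is inferred from the objective rather than named as a test. Relatives are the definite source of controls, with employees and students optional, so a 25-year gap in mean age may be unlikely. The large figures need both that gap and the steeper slope. The adjusted rates near 5% are largely built in, because the simulated age effect is linear or nearly so. Age must be ascertained for eligibility, and nothing shows that sex goes unrecorded.

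Much of this stands, and it limits the weight of the point. It does not answer it. The aim of describing what is altered in chronic pain is written into Objective I, and the plan commits to nothing that would separate that from age or sex. Spouses and relatives guard partly on age but need not balance sex. Leaving adjustment to be decided after the data are seen adds analytic freedom of its own.

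**Conclusion.** The concern holds. The plan declines matching and specifies no adjustment, so the patient-versus-healthy comparison under Objective I is open to confounding by age and sex. Whether bias will occur cannot be known from the documents: it needs both an imbalance and an outcome that depends on the unbalanced factor.

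On the assumed inputs, the effect ranges from none (equal nominal mean ages and balanced sex, about 5% false positives) to serious (0.43 SD and 42% from age alone at 35 per group; 55% with a sex effect in the same direction). One patient age distribution stands in for several different pain groups. The within-subject stimulus contrast is untouched, and the exploratory status lowers the stakes without removing the bias. The plan should be changed on this point, but it does not undermine the study.

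**What to change.** - Keep age and sex in the analysis data for every Objective I participant, patient and healthy.
- In Section 7, state that each patient-versus-healthy comparison will use linear or generalized linear regression with group, age (continuous) and sex as terms.
- Report age and sex by group, and repeat each comparison within the overlapping age range as a check.
- State that adjustment may not remove bias from non-linear age effects or from other group differences such as medication.
- Optionally, monitor age and sex by group during recruitment. This limits the precision loss, but it would mean revising the Section 5 statement and could slow enrolment.

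Matching is not required, and no visit or procedure is added. The cost is analysis-plan wording, keeping sex alongside the age already needed for eligibility, and precision. On the assumptions above, with balanced sex, the adjusted standard error is larger by 2% to 5% at nominal mean ages 60 v 55, 17% to 21% at 60 v 45 and 43% to 48% at 60 v 35. With 80% v 50% women the figures are 7% to 10%, 21% to 25% and 46% to 52%. With equal nominal mean ages and balanced sex the change is about 0% to 2%. The overlap check also discards data: at 60 v 35 it keeps about 24 patients and 16 controls of 35 each, or about 11 and 8 of 20 each. The fix is therefore least precise where the imbalance is greatest, which is the argument for watching the groups during recruitment.
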